6.2 Treatment Administration

Patients currently receiving or about to start treatment with an oral tyrosine kinase inhibitor for one of the major oncogenic drivers (EGFR, MET, BRAF, V600E, RET, HER2, Alk, or ROS-1) will be eligible. At the time of registration, blood samples will be obtained for plasma and other biomarker analyses (Appendix J), tobacco use (Appendix D) and performance status (Appendix K) will be determined. Treatment with an agent targeting the primary oncogenic driver will be continued until progression. If a new agent is approved for treatment of the primary driver, patients may be changed prior to progression at the investigator's discretion.

At the time of progression, patients will undergo repeat biopsy to determine PD-L1 staining and large scale genetic testing. Foundation Medicine testing is preferred but patients may have testing performed by other platforms including Guardant 360. Other platforms may be used after discussion with the principal investigator. Research plasma and tissue will be collected (Appendix J). Patients will also complete a detailed tobacco use questionnaire at the time of progression (Appendix E). Further, Performance Status will be determined (Appendix K). While awaiting results of testing, patients may continue the current treatment targeting the primary oncogenic driver.

Phase II Pilot Study Evaluating Strategies to Overcome Resistance at the Time of Progression
for Patients with Non-Small Cell Lung Cancers Harboring Major Oncogenic Drivers
Wake Forest Baptist Comprehensive Cancer Center (CCCFWU)
CCCFWU 62716
ClinicalTrials.gov: NCT02949843

If the PD-L1 testing result is $\geq 50\%$, patients will receive immunotherapy with either nivolumab or pembrolizumab as subsequent treatment. If patients have PD-L1 testing result that is $< 50\%$, the large scale testing will be used to determine the presence of absence of a secondary driver. For the purposes of the study, a secondary oncogenic driver will be considered an activating genetic change in a gene other than the primary oncogenic driver gene that has an effective treatment. These would include EGFR, Alk, ROS-1, MET, BRAF V600E, RET, and HER2. Classification of a genetic alteration as a secondary driver will be determined by the investigator.

For patients without secondary oncogenic drivers, treatment will be categorized as subsequent line of treatment, targeting the primary oncogenic driver, or other treatment. For patients with secondary oncogenic drivers, treatment will be categorized as treatment targeting secondary oncogenic driver, subsequent line of treatment targeting the primary oncogenic driver or other treatment. Targeted treatments may include those treatments listed on NCCN Guidelines. Initial medication dose and dose modifications should be implemented according to standard of care guidelines.

Treatment will be administered on an inpatient or outpatient basis. Reported adverse events and potential risks are described in Section 9.0. No investigational or commercial agents or therapies other than those described below may be administered with the intent to treat the patient's malignancy.

6.2.1 Other Studies/Procedures

In relation to additional or optional tissue contribution for study subjects, all subjects will have blood taken at study entry and tumor biopsies and/or blood draws for plasma isolation at the time of first progression after initial driver mutation targeted therapy. If they choose to allow a portion of that tissue to be used for future research it will be stored in the below location:

All samples and specimens should be shipped to:
Wake Forest Cancer Center
Tumor Tissue Core Facility
Care of [name]
[name]
[name]
[name]

6.2.2 Premedication regimen and concurrent medications

Anti-emetics:

Anti-emetics should consist of standard 5HT3 antagonist medications at the investigators discretion. Use of corticosteroids as prophylactic anti-emetics should generally be avoided and reasons for the use of these drugs as pre-medications should be documented.

6.3 General Concomitant Medication and Supportive Care Guidelines

Patients should receive *full supportive care*, including transfusions of blood and blood products, erythropoietin, antibiotics, antiemetics, etc., as clinically indicated. Anti-inflammatory or narcotic analgesics may be offered as needed. Medications considered necessary for the patient's well-being may be given at the discretion of the investigator, i.e., chronic treatments for concomitant medical conditions, as well as agents required for life-threatening medical problems, etc. The reason(s) for treatment, dosage, and dates of treatment should be recorded on the flow sheets.

6.4 Duration of Therapy

The duration of the research treatment is through the first follow-up CT scan after the addition of second-line treatment with nivolumab or pembrolizumab. Treatment may continue beyond this point at the investigator's discretion. In the absence of treatment delays due to adverse events, treatment may continue until one of the following criteria applies:

- Disease progression,
- Intercurrent illness that prevents further administration of treatment,
- Unacceptable adverse event(s), specifically if Grade 3 or 4 neurotoxicity is observed
- Patient decides to withdraw from the study, or
- General or specific changes in the patient's condition render the patient unacceptable for further treatment in the judgment of the investigator.

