6.6 Criterial for Removal from Study

Patients will be removed from the study when any of the criteria listed in section 6.4 are met.

Dose Delays/Modifications

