6.7 Recommended Dose Modifications for Nivolumab (OPDIVO™)

Table 1: Adverse Reaction	Severity	Dose Modification
Colitis	Grade 2 diarrhea or colitis	Withhold dose ^a
	Grade 3 diarrhea or colitis	
	Single-agent OPDIVO	Withhold dose ^a
	OPDIVO, in combination with ipilimumab	Permanently discontinue
	Grade 4 diarrhea or colitis	Permanently discontinue
Pneumonitis	Grade 2 pneumonitis	Withhold dose ^a
	Grade 3 or 4 pneumonitis	Permanently discontinue
Hepatitis	Aspartate aminotransferase (AST)/or alanine aminotransferase (ALT) more than 3 and up to 5 times the upper limit of normal or total bilirubin more than 1.5 and up to 3 times the upper limit of normal	Withhold dose ^a
	AST or ALT more than 5 times the upper limit of normal or total bilirubin more than 3 times the upper limit of normal	Permanently discontinue
Hypophysitis	Grade 2 or 3 hypophysitis	Withhold dose ^a
	Grade 4 hypophysitis	Permanently discontinue
Adrenal Insufficiency	Grade 2 adrenal insufficiency	Withhold dose ^a
	Grade 3 or 4 adrenal insufficiency	Permanently discontinue
Nephritis and Renal Dysfunction	Serum creatinine more than 1.5 and up to 6 times the upper limit of normal	Withhold dose ^a
	Serum creatinine more than 6 times the upper limit of normal	Permanently discontinue
Rash	Grade 3 rash	Withhold dose ^a
	Grade 4 rash	Permanently discontinue
Encephalitis	New onset moderate or severe neurologic signs or symptoms	Withhold dose ^a
	Immune-mediated encephalitis	Permanently discontinue
Other	Other Grade 3 adverse reaction	
	First occurrence	Withhold dose ^a
	Recurrence of same Grade 3 adverse reactions	Permanently discontinue
	Life-threatening or Grade 4 adverse reaction	Permanently discontinue
	Requirement for 10 mg per day or greater prednisone or equivalent for more than 12 weeks	Permanently discontinue
	Persistent Grade 2 or 3 adverse reactions lasting 12 weeks or longer	Permanently discontinue

^a Resume Treatment when adverse reaction returns to Grade 0 or 1

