6.8 Recommended Dose Modification for Pembrolizumab (Keytruda)

Withhold KEYTRUDA for any of the following:

Grade 2 pneumonitis [see *Warnings and Precautions (5.1) of FDA insert*]

Grade 2 or 3 colitis [see *Warnings and Precautions (5.2) of FDA insert*]

Grade 3 or 4 endocrinopathies [see *Warnings and Precautions (5.4) of FDA insert*]

Grade 2 nephritis [see *Warnings and Precautions (5.5) of FDA insert*]

Aspartate aminotransferase (AST) or alanine aminotransferase (ALT) greater than 3 and up to 5 times upper limit of normal (ULN) or total bilirubin greater than 1.5 and up to 3 times ULN

Any other severe or Grade 3 treatment-related adverse reaction [see *Warnings and Precautions (5.6) of FDA insert*]

Resume KEYTRUDA in patients whose adverse reactions recover to Grade 0-1.

Permanently discontinue KEYTRUDA for any of the following:

Any life-threatening adverse reaction (excluding endocrinopathies controlled with hormone replacement therapy)

Grade 3 or 4 pneumonitis or recurrent pneumonitis of Grade 2 severity [see *Warnings and Precautions (5.1) of FDA insert*]

Grade 3 or 4 nephritis [see *Warnings and Precautions (5.5) of FDA insert*]

AST or ALT greater than 5 times ULN or total bilirubin greater than 3 times ULN

For patients with liver metastasis who begin treatment with Grade 2 AST or ALT, if AST or ALT increases by greater than or equal to 50% relative to baseline and lasts for at least 1 week

Grade 3 or 4 infusion-related reactions [see *Warnings and Precautions (5.7) of FDA insert*]

Inability to reduce corticosteroid dose to 10 mg or less of prednisone or equivalent per day within 12 weeks

Persistent Grade 2 or 3 adverse reactions (excluding endocrinopathies controlled with hormone replacement therapy) that do not recover to Grade 0-1 within 12 weeks after last dose of KEYTRUDA

Any severe or Grade 3 treatment-related adverse reaction that recurs [see *Warnings and Precautions (5.6) of FDA insert*]

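### For a first Grade 3 neurologic event that recovers to Grade 0 or 1, sections 6.4 and 6.6 end treatment and remove the patient, while sections 6.7 and 6.8 withhold the drug and resume it

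*Combined protocol and SAP*

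**What the plan says.** Four sections of the combined protocol and SAP bear on this event.

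- **Section 6.4, Duration of Therapy.** The list of end points for treatment is introduced by "In the absence of treatment delays due to adverse events, treatment may continue until one of the following criteria applies". One item is "Unacceptable adverse event(s), specifically if Grade 3 or 4 neurotoxicity is observed". It makes no exception for a first occurrence or for recovery.
- **Section 6.6, removal from study.** "Patients will be removed from the study when any of the criteria listed in section 6.4 are met".
- **Section 6.7, nivolumab table.** Within the Encephalitis entry, "New onset moderate or severe neurologic signs or symptoms" leads to withholding the dose, and "Immune-mediated encephalitis" leads to permanent discontinuation. Within the entry for other reactions, the first occurrence under "Other Grade 3 adverse reaction" leads to withholding, while "Recurrence of same Grade 3 adverse reactions" leads to permanent discontinuation. The footnote on every withheld dose says to resume at Grade 0 or 1.
- **Section 6.8, pembrolizumab.** There is no neurologic entry. The drug is withheld for "Any other severe or Grade 3 treatment-related adverse reaction", resumed on recovery to Grade 0-1, and stopped for good if such a reaction recurs.

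Section 6.5 follows every patient until death for survival, and follows those removed for unacceptable adverse events until the event resolves or stabilizes. It does not mention response imaging after removal.

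**The concern.** An investigator whose patient has a first Grade 3 neurologic event finds one instruction in the general treatment rules and a different one in the section for the drug being given. If the event settles, the first has already taken the patient off treatment and off study, while the second has the patient back on drug. Two investigators could each follow the protocol and manage the same safety event differently.

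The drugs concerned are the two used in the arm with PD-L1 expression of at least 50%, which carries the primary endpoint. A patient removed early may have no later scan from which a response could be recorded. A patient who resumes treatment stays on the imaging schedule.

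**Working it through.** The plan states no figure on this point, so the check is a comparison of the texts, case by case.

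| Event | Sections 6.4 and 6.6 | Section 6.7 or 6.8 | Conflict? |
|---|---|---|---|
| First Grade 3 neurologic event on nivolumab, not immune-mediated encephalitis, recovering to Grade 0 or 1 | End treatment, remove from study | Withhold, then resume | Yes |
| First Grade 3 treatment-related neurologic event on pembrolizumab, recovering to Grade 0-1 | End treatment, remove from study | Withhold, then resume | Yes |
| Recurrence of the same Grade 3 reaction, either drug | End treatment | Permanently discontinue | No |
| Immune-mediated encephalitis of Grade 3 or 4 on nivolumab | End treatment | Permanently discontinue | No |
| Grade 4 neurologic reaction on nivolumab | End treatment | Permanently discontinue | No |
| Life-threatening neurologic reaction on pembrolizumab | End treatment | Permanently discontinue | No |

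**Basis for the first row.** Two entries in section 6.7 lead to withholding. The more general is the first occurrence of another Grade 3 reaction. The other is the row for new neurologic signs. That row sits under Encephalitis and is worded by severity (moderate or severe), not by grade, so it is not a general rule for Grade 3 neurotoxicity. The conflict does not depend on it: a Grade 3 neurologic event outside the Encephalitis entry falls under the other-reaction row.

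**Basis for the second row.** Since section 6.8 has no neurologic entry, the conflict arises only through its general entry, which covers treatment-related reactions. Section 6.4 contains no such restriction.

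**Consequences for data.** Under section 6.5 removal does not end survival follow-up, so overall survival is protected. Under section 7.1 the response rate is the proportion of subjects with a complete or partial response. Nothing there discards a response recorded before removal or drops a removed patient from the denominator. What remains open is imaging after removal. Footnote d of the table in section 6.1 fixes the first two scans at 8-week intervals on nivolumab (8 and 2 × 8 = 16 weeks) and 9-week intervals on pembrolizumab (9 and 2 × 9 = 18 weeks). No section says whether these are still done in a patient removed before them.

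**Scale.** Each patient is 1/15 = 6.7% of the primary arm. The documents give no rate for Grade 3 neurotoxicity on either drug.

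**The case against.** The strongest reply is that the sections can be read in order of authority. Section 6.4 names neurotoxicity, whereas the pembrolizumab entry and the nivolumab other-reaction row are residual categories, and a specific rule would normally override a residual one. Sections 6.7 and 6.8 are headed as recommendations, while section 6.6 is mandatory in tone. The 6.4 list also opens with a qualifier about treatment delays due to adverse events. This is a reasonable way to read the protocol, but nothing in the protocol states it. The qualifier provides no route to withhold and resume for neurotoxicity, and section 6.6 applies the criteria without it. Nor can the 6.4 item be set aside as meant for other agents, since that section defines the research treatment period by nivolumab or pembrolizumab.

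A second reply is that the event is probably rare, and this has some force. In section 8.2, peripheral neuropathy appears among other clinically important effects at 1-10%, and the list of Grade 3-4 effects at 1-10% has no neurologic term. If that list is complete, which is an assumption, each neurologic term has a Grade 3-4 rate on nivolumab below 1%. That means fewer than 15 × 0.01 = 0.15 expected events per term if all 15 patients received nivolumab. The pembrolizumab table in section 8.1 covers only reactions in at least 10% of patients, so it does not settle the Grade 3 rate. Rarity limits the likely effect on the endpoint; it does not make the instructions compatible.

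A reader might also infer that every Grade 3 neurotoxicity has opposite instructions, or that survival data are lost on removal. The documents support neither: the sections agree on the four cases marked as no conflict, and section 6.5 continues survival follow-up until death.

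**Conclusion.** The point stands in a narrow form. For a first Grade 3 neurologic adverse event that recovers to Grade 0 or 1, the protocol gives incompatible instructions for nivolumab and, where the event is treatment-related, for pembrolizumab. No section is said to govern. This is an inconsistency of wording in a safety instruction, not a flaw in the statistical design.

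A reader might go further and argue that the conflict could decide the trial. Under the 10% null, the two-stage design gives p = 0.173 for 3 responses in 15 (not rejected) and p = 0.0544 for 4 in 15 (rejected), so one response can change the result. The arithmetic is right, but it applies to any single patient lost for any reason and measures nothing about this conflict. For the conflict to matter, a patient would have to have the event, recover, be removed before any response was recorded, have gone on to respond if treatment had resumed, and be the deciding responder. Without an event rate, the effect on the primary arm is possible but cannot be sized.

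**What to change.** Reconcile sections 6.4 and 6.6 with sections 6.7 and 6.8 so that a first Grade 3 neurologic event has one instruction for each drug, and name the section that governs if they differ. Which instruction applies is a clinical decision for the sponsor.

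State also whether response imaging continues after a patient is removed for an adverse event. No new statement on survival is needed, because section 6.5 already covers it.

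The cost of these changes is protocol wording in an amendment. Sample size and the analysis of the primary objective are unaffected.

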6.5 Duration of Follow Up

Patients will be followed for a minimum of 30 days after the last study drug is administered for adverse events monitoring. Patients will be followed for a minimum of 30 days after removal from study or until death, whichever occurs first. Patients removed from study for unacceptable adverse events will be followed until resolution or stabilization of the adverse event. Patients will be followed until death for monitoring survival study endpoints.

6.6 Criterial for Removal from Study

Patients will be removed from the study when any of the criteria listed in section 6.4 are met.

Dose Delays/Modifications

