6.0 Treatment Plan

6.1 Study-Related Interventions

	Pre-Study ^a	At Each Treatment	After First-Progression	Follow-up
Informed consent	X			
Demographics	X			
Medical history	X			
Concurrent meds	X			
Physical exam	X		X	X
Vital signs	X		X	X
Height, Weight, M ²	X			
Performance Status	X		X	X
Tumor measurements			X	X ^d
CBC w/diff, platelets	X	X	X	X
Serum chemistry ^b	X	X	X	X
B-HCG ^c	X			
Adverse event evaluation		X	X	X
Tobacco Use Assessment	X		X	
Research blood (plasma)	X		X	
Tumor Biopsy			X	

a: Pre-study requirements listed in table must be completed **within** 14 days prior to registration.
 b: Alkaline phosphatase, total bilirubin, BUN, calcium, creatinine, SGOT[AST], SGPT[ALT]
 c: Serum pregnancy test (women of childbearing potential).
 d: After the patient receives first dose of study drug they should be followed for progression on the following time line: for patients receiving nivolumab, imaging should be performed every 8 weeks +/- 3 days for the first two imaging studies. For patients receiving pembrolizumab, imaging should be performed every 9 weeks +/- 3 days for the first two imaging studies. After the first two imaging studies, additional follow-up imaging interval will be at the investigator's discretion. For patients receiving other treatments, all follow-up imaging intervals will be at the investigator's discretion.

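### Section 6.6 makes stopping treatment a reason to leave the study and conflicts with the scan schedule in 6.1 footnote d, so a patient who stops immunotherapy early without progression can leave before the primary-endpoint scan

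*Combined protocol and SAP*

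**What the plan says.** **Removal.** Section 6.6: "Patients will be removed from the study when any of the criteria listed in section 6.4 are met".

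**The criteria it points to.** The list in 6.4 governs how long treatment may continue. Besides progression and patient withdrawal, it contains "Intercurrent illness that prevents further administration of treatment", "Unacceptable adverse event(s), specifically if Grade 3 or 4 neurotoxicity is observed", and changes in condition that "render the patient unacceptable for further treatment in the judgment of the investigator". The same section opens with the intended treatment period: "The duration of the research treatment is through the first follow-up CT scan after the addition of second-line treatment with nivolumab or pembrolizumab".

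**Follow-up after removal.** Section 6.5 sets a minimum of 30 days after removal (or until death, if sooner) and survival follow-up until death. For toxicity it adds "Patients removed from study for unacceptable adverse events will be followed until resolution or stabilization of the adverse event". Tumour imaging is not mentioned.

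**Scans.** Footnote d of the 6.1 schedule begins "After the patient receives first dose of study drug they should be followed for progression on the following time line". For nivolumab, "imaging should be performed every 8 weeks +/- 3 days for the first two imaging studies"; for pembrolizumab the interval is 9 weeks with the same tolerance. Later scans, and all scans for patients on other treatments, are left to the investigator. The schedule marks tumour measurements in its Follow-up column.

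**Endpoint.** Section 7.1 defines objective response as the proportion of subjects with complete or partial response. Section 12.2 tests it in the PD-L1 ≥50% arm: stop if 0 of 8 respond, otherwise accrue 7 more and reject a 10% rate if at least 4 of 15 respond. Neither section says how a patient without a response scan is counted.

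**The concern.** Stopping a drug and leaving a study are different events, and 6.6 merges them. The reference in 6.5 to removal for unacceptable adverse events shows that the plan does expect removal on toxicity grounds. A patient who permanently stops immunotherapy in the first weeks without progression is then off study before response has been measured. Footnote d starts the imaging clock at first dose and does not make it depend on staying on drug, which points the other way. Two sites, or two coordinators, could follow the text in good faith and collect different primary-endpoint data.

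The arm is small. Each patient is 1/15 = 6.7 percentage points of the response rate, and the decision turns on a count of 4. One response that goes unrecorded turns 4 of 15 into 3 of 15 and reverses the conclusion. At stage 1, one unrecorded response can turn 1 of 8 into 0 of 8 and stop the study.

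**Working it through.** **1. The plan's own figures (12.2).** Inputs: n1 = 8, stop at 0; n = 15, reject at ≥4; null 10%, alternative 40%.

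P(reject) = P(X15 ≥ 4) − P(X1 = 0) × P(X2 ≥ 4), with X1 ~ Bin(8, p), X2 ~ Bin(7, p) and X15 = X1 + X2.

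- p = 0.10: 0.0556 − 0.4305 × 0.0027 = 0.0544
- p = 0.40: 0.9095 − 0.0168 × 0.2898 = 0.9046

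These match the stated 0.054 and 90.5%. The design figures are correct; they assume a response outcome for all 8 and all 15 patients.

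**2. How far the 30-day minimum reaches.** Count days from first dose and suppose, in the plan's favour, that the 30 days after removal include imaging.

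| | First target | Last stop day that misses it | Second target | Last stop day that misses it |
|---|---|---|---|---|
| Nivolumab | 8 × 7 = day 56 | before 56 − 30 = day 26 | 16 × 7 = day 112 | before 112 − 30 = day 82 |
| Pembrolizumab | 9 × 7 = day 63 | before 63 − 30 = day 33 | 18 × 7 = day 126 | before 126 − 30 = day 96 |

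The ±3-day tolerance moves the first limit to day 23 or day 30 at the earliest. A stop at week 5 (day 35) is followed to day 65, which covers both first-scan targets but neither second scan.

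**3. Effect on the design (illustration).** The documents give no share of patients stopping before the first scan. Let m be the share who leave unscanned, count them as non-responders, and assume stopping is unrelated to response. The observable rate is p × (1 − m); for example 0.40 × 0.90 = 0.36. Putting this rate into the formula in step 1:

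| m (assumed) | Observable rate if true rate is 40% | Power | P(0 of 8) at true 40% | Type I error at true 10% |
|---|---|---|---|---|
| 0 | 40% | 90.5% | 1.7% | 0.054 |
| 5% | 38% | 87.6% | 2.2% | 0.046 |
| 10% | 36% | 84.1% | 2.8% | 0.039 |
| 20% | 32% | 75.1% | 4.6% | 0.027 |
| 30% | 28% | 63.4% | 7.2% | 0.017 |

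Only patients who stop without progression and are never scanned belong in m. Those who progress or die early are genuine non-responders.

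**The case against.** The best defence is that the plan already supplies the scans. Footnote d runs from first dose, the Follow-up column marks tumour measurements, and the second sentence of 6.5 sets 30 days after removal without restricting it to safety. Section 6.5 follows patients for survival endpoints, and 7.2 lists progression-free survival under that heading. Duration of response in 7.1 runs to progression or death, not to end of treatment. All of this stands as evidence of intent. But no passage says that scans continue after removal, and 6.6 has no exception. The defence shows that the text supports two readings, and that is the problem to be resolved.

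Some stronger readings are tempting but go beyond the documents:

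- **That 6.5 ends imaging at removal.** It is silent on imaging.
- **That a patient stopping at week 5 necessarily loses the first scan.** Day 65 lies beyond both first-scan targets, so the loss is not established for that patient.
- **That a withheld dose means removal.** Section 6.4 requires an unacceptable adverse event; a dose withheld under 6.7 or 6.8 does not by itself meet it.
- **That the same scans are lost in the other two arms.** Footnote d leaves imaging on other treatments to the investigator, so there is no fixed scan to miss.
- **That the response rate will be inflated by dropping or replacing patients.** No passage does either. Section 12.2 speaks of accrued patients and decides on a count of responses.

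It is also fair to say that the power loss rests on an assumed share, and that counting unscanned patients as non-responders lowers the type I error, so that error is conservative.

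**Conclusion.** The concern holds as a conflict between 6.1 footnote d, 6.5 and 6.6 that can cost primary-endpoint data in the PD-L1 ≥50% arm. It is not a demonstrated loss, and the design calculation is not wrong. On the literal reading of 6.6, the first response scan is exposed for any non-progressed patient who stops before it. If the 30-day follow-up is taken to include imaging, the exposure narrows to stops before about day 26 (nivolumab) or day 33 (pembrolizumab), with the second scan usually still missed.

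The size depends on a share that the plan does not state. At 5% the loss of power is small (90.5% to 87.6%); at 20% it is material (75.1%). These figures assume that unscanned patients count as non-responders and that stopping is independent of response. The loss is larger if responders stop early more often than others, and smaller if less often. The remedy is cheap and should be made.

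**What to change.** Reconcile 6.1 footnote d, 6.5 and 6.6:

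1. In 6.6, separate end of treatment from removal from study. State that immunotherapy-arm patients who stop treatment for a reason other than progression, death or withdrawal of consent remain on study for the two scans already scheduled in footnote d.
2. In 6.5, add tumour assessment for these patients to the follow-up after treatment. Patients who have progressed continue in survival follow-up as 6.5 already provides.
3. In 7.1 and 12.2, state that treated patients with no post-baseline scan stay in the 8 and in the 15 as non-responders. This fixes both denominators and rules out dropping patients after the fact.

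The criteria for stopping treatment are untouched. The design keeps its 0.054 and 90.5% to the extent that the scans are obtained. The cost is amendment wording and up to two already-planned scans in a few patients who are off drug. The counting rule gives up some power for any scan still missed, without raising the type I error.
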